3.2.9 Adverse Event Reporting

We will report any unanticipated adverse device effects to Medtronic and IRB as soon as possible after the event occurs (within 10 working days after first learning about event). Evaluations of unanticipated adverse device effects will be reported to the FDA, IRB, and Medtronic within 10 days after receiving notice of effect and in accordance with guidance 812.150. We do not expect any adverse events related with the functionality of the implanted device.

3.2.10 Data Analysis

Experimental outcomes: Beta power, UPDRS III and quantitative measures of tremor (rest tremor recording for 1 minute), bradykinesia (WFE task) and FOG (using a Stepping in Place (SIP) task and gait analysis), and time DBS ON over the 30 minutes on aDBS.

Number of arms: (One) Patients will be used as their own controls.

All quantitative data will be post-processed using custom MATLAB software (The MathWorks, USA).

1. **Repetitive wrist flexion-extension movement – rwFE:** The Motus motion analysis system will be used to obtain an objective quantitative assessment of bradykinesia by measuring hand angular velocity during a quantitative repetitive wrist flexion-extension task (rwFE). The system consists of sensors in which vibrating quartz crystals act like solid-state gyroscopes and produce an analog signal whose voltage is proportional to the angular velocity when rotated about its measurement axis. These sensors are unlike conventional accelerometers in that they are indifferent to their orientation with respect to gravity. Each sensor weighs about 60 g, has a maximum range of 1,900 degrees per second, a low noise level of 1 degree per second RMS, and a flat response to 30 Hz. The angular velocity data will be digitized at a rate of 100 samples per second per sensor. The root mean square velocity of angular movement (Vrms) will be used as an indication of the average speed at which the flexion-extension task is performed. The frequency spectrum of the angular velocity will be analyzed using a fast Fourier transform (FFT) analysis in each trial to ensure that patients' movements are not dominated by a fast-action tremor (7–12 Hz).
2. **Tremorography;** Using the above mentioned angular velocity sensors, the angular velocity data during rest and/or postural poses will be digitized at a rate of 100 samples per second per sensor and the frequency spectrum will be will be analyzed using an FFT analysis to detect and quantify the type of tremor (rest 4-6 Hz or action/postural 712 Hz) that is present.
3. **Muscle activation patterns:** The Delsys Surface EMG System will be used to collect electromyography signals from the wrist flexor and extensor muscles. The signals will be filtered using a fourth-order band pass Butterworth (20-300 Hz) applied in the forward and reverse directions to prevent phase distortions. The linear envelope of the rectified signals will be calculated by finding the absolute value of the signal and then calculating the RMS value at every 50 ms. The signals will be normalized by the average of the three greatest peak values of each muscle for comparing amplitude of muscle activity within tasks for each patient and also across patients.
4. **Repetitive alternating finger tapping (RAFT) keyboard task:** The engineered keyboard outputs a calibrated analog signal that corresponding to the displacement of the keys. The downstrike velocity, interval between strikes, and duration of keystrokes will be extracted from the recorded signal.

5. **Stepping in place (SIP) task;** During the SIP task, ground reaction forces will be captured at 100 Hz with two force plates (Advance Mechanical Technology Inc, Watertown, MA, USA). A freezing episode (FE) will be defined when the patient is unable to completely lift a foot from the force plates (i.e. when the vertical forces did not reach 100% (foot in stance) and 0% (lifting phase)). FEs will be identified only if detected visually and with the computerized algorithm. The experimenter will document the occurrence of FEs to compare with the offline force plate data analysis. A computerized algorithm to automatically detect freezes will be performed in MATLAB. Signals from the force plates will first be low-pass filtered at 12 Hz with a second order Butterworth filter. Peaks reaching values below 15% and above 85% and separated by more than 400ms will be detected. If fewer than 20 peaks are detected on one of the force plates, the entire trial will be considered a FE and the analysis will be terminated. For each signal, abnormally long intervals will be defined as intervals between two maxima or two minima whose duration is longer than either 1.2 times the average duration of the intervals between the corresponding extrema in the three previous cycles, or longer than twice the average interval duration in the whole trial. A FE will be defined as an episode of abnormally long intervals detected concurrently on the two force plates. Finally, using the same criterion as for visual detection, when fewer than four minima and fewer than four maxima on each force plate (fewer than three strides) separated two FEs, these will be combined into a long FE. The stepping cycle symmetry and rhythmicity of SIP will be calculated for the first 25 s of each SIP trial and will be averaged over the three trials. According to previous studies, asymmetry and rhythmicity were defined as: SIP cycle asymmetry = $100 \times [\ln(\text{SSWT}/\text{LSWT})]$, where SSWT and LSWT correspond to the leg with the shortest and longest mean swing time over the trials, respectively and rhythmicity = the mean stride time coefficient of variation (CV) of both legs. A large stride time CV would be indicative of a less rhythmic gait.
6. **Gait Analysis:** Standard quantitative gait metrics including but not limited to freezing episode duration, gait speed, gait asymmetry, gait rhythmicity, swing phase and left-right step coordination.
7. **Speech Analysis:** Audio recordings of the speech tasks will be analyzed to obtain metrics that include but are not limited to diadochokinesis rate, speaking rate, intelligibility rate, and communication efficiency ratio.

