3.2.3 Study Design, Setting/Location

This is an open-label pilot study of up to 30 people with Parkinson's disease. All experiments will be performed in the Stanford Human Motor Control and Balance Laboratory in the department of Neurology and Neurological Sciences at Stanford University Medical Center. A unique aspect of the Stanford Movement Disorders Center is the Stanford Human Motor Control and Balance Laboratory, in which we have developed several quantitative measures of motor control and a parallel line of research in human motor control in movement disorders. These measures have been validated with the clinical scale most widely used in PD research, the UPDRS III, as stated above.

Study Population

The study will be carried out in up to 30 people with moderate to advanced PD who will have been evaluated and approved to have subthalamic deep brain stimulation to treat their motor signs. Subjects who have been implanted with Activa PC+S and are participating or have completed Study 1 will be asked to complete Study 2. In order to account for study attrition additional subjects (up to 30) will be recruited into study 2.

Battery life on the Activa PC + S (research device) and the Activa PC (FDA-approved clinical device) is estimated to last approximately 3-5 years. A limited number of subjects will be invited to be replaced with an Activa PC+S, should they chose to remain in the study. Invitations to receive a replacement Activa PC+S will depend on the focus of future experiments, quality of signal, and device availability. If the patient would prefer not to continue in the study, or if they are not invited to continue, they may proceed with the standard implantation of the non-research device.

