3.2.5 Study outcomes

Beta power, UPDRS III, and quantitative measures of tremor (rest tremor recording for 1 minute), bradykinesia (WFE task), speech and FOG (using a Stepping in Place (SIP) task⁴/Gait Analysis), and time DBS ON over the time on aDBS.

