8. An interval history, examination, and UPDRS III will be performed. LFPs will be recorded from the DBS leads during some of the clinical assessments such as the repetitive wrist flexion-extension task and during stepping in place.
9. Real-time STN LFP beta band power will be calculated both on medication/OFF DBS, and during “therapeutic” DBS. DBS will be applied through the electrode (1 or 2) that lies in between the electrode pair (0-2 or 1-3) with the greatest beta power. Therapeutic DBS: 140 Hz, 60 microsec at 3 volts OR the highest voltage <3V that does not cause adverse effects.
10. We will confirm that the therapeutic DBS will attenuate rest beta power by $\geq 40\%$ ⁴.
11. Patients will be seated at rest, or while performing self-paced repetitive wrist flexion-extension (WFE) for periods of 10 seconds, after a “Go” signal with angular velocity sensors attached to the hand.
12. SA3: Determination of classifier thresholds: 1. Resting or movement state neural: ON and OFF triggers when the LFP band power or variability is greater than or less than different thresholds of the resting or movement state LFP power differential (LFP power OFF – ON therapeutic DBS). 2. Kinematic (tremor/bradykinesia): ON and OFF triggers when rectified tremor amplitude/root mean square angular velocity (Vrms) of WFE is greater than or less than different thresholds of tremor/Vrms differential (OFF – ON therapeutic DBS) respectively.
13. Outcomes will be measured during trials up to 8 hours of aDBS or cDBS. For neural and tremor aDBS, the Activa® PC+S will be updated in real time (see delays). For bradykinesia aDBS, the Activa® PC+S will be updated with the Vrms from 10-60 second epochs of WFE that the PD subject will perform throughout during the trial (rwFE, angular velocity sensors, Motus Motion analysis system, and EMG).

Blinding: The PD subject, investigators (certified) performing the UPDRS III, and investigator analyzing data will be blinded to the type of DBS used for a particular experiment. All experiments will be videotaped and two additional independent certified raters will rate the UPDRS III.

Randomization: The order of aDBS, cDBS, and all motor tasks will be randomized for each subject and enough time will be given in between for patient rest and for return to baseline of beta power, tremor, and bradykinesia.

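### Freezing episodes in the stepping-in-place task need visual confirmation by an experimenter whose blinding to the DBS condition is not stated

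*Combined protocol and SAP*

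**What the plan says.** Section 3.2.10, item 5, sets the counting rule for the stepping-in-place task: "FEs will be identified only if detected visually and with the computerized algorithm". The next sentence names who records: "The experimenter will document the occurrence of FEs to compare with the offline force plate data analysis".

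The same item contains two statements with no visual step. A trial with under 20 peaks on one plate is treated as a single freezing episode in full. Later, an episode is defined purely by overlong step intervals that occur on both plates at once.

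On blinding, section 3.2.7 states: "The PD subject, investigators (certified) performing the UPDRS III, and investigator analyzing data will be blinded to the type of DBS used". It adds: "All experiments will be videotaped and two additional independent certified raters will rate the UPDRS III". No rater is assigned to freezing. Section 3.2.3 describes the design in these words: "This is an open-label pilot study of up to 30 people with Parkinson's disease".

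Freezing of gait is among the kinematic measures in Specific Aim 1 (section 3.2.2). It is listed as an outcome in sections 3.2.5 and 3.2.10, assessed by stepping in place and by gait analysis.

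**The concern.** The counting rule joins an objective detector and a human one, and both must agree. The human one is therefore a filter on the force-plate result. If the person applying it knows whether aDBS or cDBS is running, expectation can affect which episodes are written down. Blinding the analyst does not repair this, because the analyst can only match force-plate events to a log that already exists.

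The filter may matter in practice. The algorithm can flag an interval only 1.2 times the mean of the three preceding cycles, if both plates agree. It is my inference, not a statement in the plan, that prolongations this mild leave room for judgement.

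The number of people who contribute episodes is also small. The plan enrols up to 30 subjects and tries to recruit equal numbers with and without documented freezing, so about 30 / 2 = 15 would be freezers if both targets are met. A few discretionary calls could move a within-subject comparison of that size.

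**Working it through.** The plan states no figure on this point, so there is nothing to reproduce. The check has two parts.

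**1. The text, set side by side**

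| Question | Where | Answer |
|---|---|---|
| What makes an episode count? | 3.2.10, item 5 | Visual and algorithm detection together |
| Who records it? | 3.2.10, item 5 | The experimenter |
| Who is blinded? | 3.2.7, Blinding | Subject, UPDRS III investigators, data analyst |
| What do the extra raters score? | 3.2.7, Blinding | UPDRS III only |
| Is blinded reading of freezing stated? | Nowhere | Not stated |

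The wording contrasts the experimenter's record with an offline force-plate analysis, so live recording is the natural reading, though it is not spelled out.

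**2. How unequal recording would appear in the result**

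Let A be the number of episodes the algorithm detects in a condition, and v the share of them that the observer also records. Under the joint rule:

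counted episodes = A × v

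If there is no true difference and the algorithm behaves the same in both conditions, A cancels:

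apparent ratio (aDBS / cDBS) = v(aDBS) / v(cDBS)

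spurious reduction = 1 − v(aDBS) / v(cDBS)

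The documents give no confirmation rates. Every v below is an assumption.

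| v, cDBS | v, aDBS | Ratio | Spurious reduction |
|---|---|---|---|
| 0.95 | 0.95 | 1.000 | 0% |
| 0.95 | 0.90 | 0.947 | 5.3% |
| 0.95 | 0.85 | 0.895 | 10.5% |
| 0.95 | 0.80 | 0.842 | 15.8% |
| 0.95 | 0.70 | 0.737 | 26.3% |
| 0.90 | 0.80 | 0.889 | 11.1% |

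The direction could also reverse. With 0.95 for aDBS and 0.90 for cDBS, the ratio is 0.95 / 0.90 = 1.056, a spurious increase of 5.6%.

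The table shows how the mechanism works. It does not estimate what will happen in this study.

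**The case against.** The strongest reply is that silence is not unblinding. The experimenter is not a defined role, and the person documenting episodes could be one of the blinded investigators. Someone has to know the condition in order to run the system: section 3.3 says the clinician who implements the host application makes the stimulation decisions. No section says that this person scores freezing. A reader might infer from the open-label label and the list of blinded roles that the observer knows the condition. The documents do not support that. They show only that blinding of this step is not stated. This part of the objection stands.

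Three more points stand in part:

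- **Scope.** A reader might take the whole freezing outcome to be exposed. The rule governs episode identification in stepping in place only. Asymmetry and rhythmicity need no visual call, and the gait-analysis item does not state this rule.
- **An absolute veto.** A reader might conclude that the observer can always overrule the plates. The whole-trial rule and the plate-only definition leave that unclear.
- **Benefit of the joint rule.** Visual confirmation guards against algorithm false positives. The algorithm in turn stops an observer adding episodes that it rejects. The exposure is therefore mainly to episodes not being recorded.

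On weight, the study is a pilot, and the power calculation in section 3.2.6 uses beta power, UPDRS and Vrms, not freezing episodes. That supports a low severity. It does not remove the gap, because under the stated rule a lost episode cannot be recovered by any blinded role.

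**Conclusion.** The point holds in a limited form. The stepping-in-place episode count depends on a visual record made by a person whose blinding is not stated, so selective non-recording in one condition could bias aDBS against cDBS on that count.

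The size is unknown. It is zero with equal confirmation rates and a 5% to 26% spurious reduction under the assumed 95% versus 90% to 70%. These figures assume no true difference and equal algorithm performance in both conditions. None of the rates comes from the documents, so no single value, such as the 11% from 80% versus 90%, should be read as the expected bias. Low severity; a cheap improvement.

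**What to change.** 1. In section 3.2.7 or 3.2.10, state that visual confirmation of stepping-in-place freezing is made from the existing video by a rater already in the plan, explicitly blinded to the DBS condition and to the algorithm output. Two details need care. The additional raters are called independent but are not separately stated to be blinded. If the blinded analyst scores the video, scoring should be finished before that person sees the algorithm result, or a different person should do it.
2. Report algorithm-only freezing episodes as a sensitivity analysis, with visual-algorithm agreement shown separately for each condition. Agreement that differs by condition would be a warning sign, though not proof of bias, since algorithm false positives could also differ.
3. Reconcile the joint-detection rule in item 5 with the under-20-peaks rule and the plate-only definition, stating for each whether visual confirmation is needed.

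The cost is a few sentences and some video-scoring time. The video and the algorithm output are already part of the plan.

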3. **Repetitive alternating finger tapping (RAFT) keyboard task:** RAFT is a computerized objective measure of movement velocity, speed of movement, and timing using an engineered keyboard (Quantitative DigiGraphy) with two adjacent keys. The subject will alternatively finger tap (trill) on the keyboard. The test will be performed twice for each hand. The patient will be seated at a table on which the keyboard is placed with the hand that does not perform the task placed in his/her lap. The subject will be instructed to tap as fast as s/he can while maintaining the alternating movement. This test will quantify a set of movement abnormalities seen in Parkinson's disease patients such as bradykinesia, freezing of movement, tremor, or fatigue.

4. **Stepping in place (SIP) task:** The subject will be asked to step in place repetitively on two adjacent force plates (Smart EquiTest, Neurocom Inc) with each foot on each forceplate. The subject will step at a speed similar to his/her normal walking. A baseline quiet stance will be acquired at the beginning and the end of the test. The subject will wear a harness to protect him/her from falling. This test will quantify measures such as gait asymmetry, gait rhythmicity, and left-right step coordination. These metrics may provide clues to underlying mechanisms involved in freezing of movement in PD. Our lab showed that the SIP metric has a high sensitivity (93%) and specificity (87%) for identifying freezers from non-freezers⁵.
5. **Unified Parkinson's Disease Rating Scale part III – Motor Examination (UPDRS III):** The clinical motor assessment of the subject will be performed using the UPDRS III scale.
6. **Gait Analysis:** Subjects will wear sensors on their hands, arms, chest, trunk, feet and legs (Opal sensors, APDM, Inc). These tasks will quantify measures such as gait asymmetry, gait rhythmicity and left-right step coordination during subjects normal walking. Subjects may be asked to do regular forward walking as well as walking around obstacles (such as chairs, or small room dividers) **or turning in place**. These obstacles **and turning in place** will be used in order to elicit freezing, which often occurs in constrained spaces. This type of freezing is frequently encountered in subjects' daily lives. Subjects will be monitored carefully by research team in order to ensure their safety and comfort.

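### The stepping-in-place algorithm has no rule for a freeze that is open at the start or end of the trial: such a freeze scores zero, or the whole trial if fewer than 20 peaks remain

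*Combined protocol and SAP*

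**What the plan says.** All the detection rules are in section 3.2.10 Data Analysis, item 5.

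- **Concept.** An FE is an inability to lift a foot fully off the plate. The concept does not require that stepping resumes.
- **Extrema.** "Peaks reaching values below 15% and above 85% and separated by more than 400ms will be detected".
- **Long interval.** "abnormally long intervals will be defined as intervals between two maxima or two minima whose duration is longer than either 1.2 times the average" of the corresponding intervals in the three preceding cycles, "or longer than twice the average interval duration in the whole trial".
- **Both plates.** "A FE will be defined as an episode of abnormally long intervals detected concurrently on the two force plates".
- **Both methods.** "FEs will be identified only if detected visually and with the computerized algorithm".
- **Fallback.** "If fewer than 20 peaks are detected on one of the force plates, the entire trial will be considered a FE", and analysis of that trial stops.
- **Merging.** Two FEs with too few steps between them are joined. This acts only on FEs already found.

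Section 3.2.8, item 4, describes the edges of the recording: "A baseline quiet stance will be acquired at the beginning and the end of the test". Freezing of gait measured by SIP is a listed outcome (3.2.5 and 3.2.10) and belongs to the comparison of adaptive (aDBS) with continuous (cDBS) stimulation in SA1 (3.2.2).

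**The concern.** The concept of an FE covers a patient who freezes and stays frozen until the task ends, and one who cannot start. The algorithm covers neither. In the first case no closing extremum exists, and in the second no opening one. Quiet stance, with weight on both feet, should not cross the 15% or 85% limit and so should not supply the missing extremum. Because both methods must agree, an observer who plainly sees the freeze cannot have it counted.

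The fallback does not repair this. It replaces a score of zero by the full trial length once the peak count falls below 20, so two nearly identical trials can receive opposite scores. Patients are their own controls, the pilot is small (up to 30 people, 3.2.3), and item 5 averages its symmetry and rhythmicity measures over only three SIP trials. A few mis-scored trials could therefore move a patient's aDBS versus cDBS difference.

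**Working it through.** The plan states no figure to reproduce. Item 5 gives the filter, thresholds, interval limits, two-plate rule and fallback. The following are assumptions: stride 1.1 s (range 0.9 to 1.4 s), trial lengths of 30 to 100 s, and plate force between 15% and 85% during a freeze. Item 5 does not say whether the 20 peaks are maxima plus minima or one type only, so both readings are used.

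**1. Is an edge freeze found?** Item 5 was coded as written and run on simulated two-plate signals containing one 10 s freeze, 100 trials for each position, at 60 s and again at 90 s:

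- mid-trial: found in 100 of 100
- running to trial end: 0 of 100
- before the first step: 0 of 100

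**2. When does the fallback act?** A stride gives one maximum and one minimum per plate.

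- Maxima plus minima: 20 / 2 = 10 strides, and 10 × 1.1 = 11 s of stepping (9 to 14 s over the stride range).
- One type only: 20 × 1.1 = 22 s (18 to 28 s).

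**3. How does the score behave around that cut?** Freeze from onset to the end of a 60 s trial:

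| Onset | Truly frozen | Scored, maxima plus minima | Scored, one type |
|---|---|---|---|
| 10 s | 50 s | 60 s | 60 s |
| 12 s | 48 s | 0 s | 60 s |
| 20 s | 40 s | 0 s | 60 s |
| 22 s | 38 s | 0 s | 0 s |

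In a 30 s trial, a 10 s edge freeze leaves about 20 / 1.1 = 18 maxima and 18 minima. It scores 0 s under the first reading (36 peaks) and 30 s under the second (18 peaks).

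**4. What happens to a contrast between conditions?** Assume exponential durations and trials that begin in stepping. The worse condition has 10 s freezes per 15 s of stepping, the better one 5 s freezes per 20 s.

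- Share of trials that end frozen: 10 / 25 = 40% against 5 / 25 = 20%.
- Expected open freeze time lost: 0.40 × 10 = 4 s against 0.20 × 5 = 1 s, so the contrast loses about 3 s before the fallback acts.

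Simulation of 20,000 trials per setting, with fallback trials kept at full length; the percentages show the spread over repeat runs:

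| Trial | True difference | Scored, maxima plus minima | Scored, one type |
|---|---|---|---|
| 30 s | 4.5 s | 4.2 s (-2% to -10%) | 7.2 s (about +60% to +70%) |
| 60 s | 10.6 s | 8.0 s (-22% to -25%) | 10.7 s (-4% to +2%) |
| 100 s | 18.5 s | 15.5 s (-15% to -17%) | 15.8 s (-13% to -15%) |

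At 100 s the fallback hardly acts, and the hand calculation agrees: 3 / 18.5 = 16%. In shorter trials the fallback adds time back, mostly in the worse condition, and offsets or outweighs the loss.

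These runs cover freezes open at trial end. The mechanism for start hesitation is shown in step 1, but its effect on the contrast was not sized.

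**The case against.** A reader might infer that the worse condition is always under-counted and that the contrast always shrinks. The documents do not support that. The fallback over-scores the most severe trials, and the net effect depends on a trial length and a peak definition that the plan does not give. Ignoring the fallback would put the loss at 60 s at 3 / 10.6 = 28%, but that leaves out exactly the trials that push the other way.

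Other points against, and what stands of each:

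- **Summary measure.** The plan does not say whether SIP freezing is summarised as a count, a duration or percent time. Asymmetry and rhythmicity use only the first 25 s and do not depend on FE scoring. This stands, so the effects in seconds are illustrations. A missed edge freeze would still be wrong in any of the three summaries.
- **Validated task.** Section 3.2.8 cites 93% sensitivity and 87% specificity for SIP. Those figures concern telling freezers from non-freezers, not measuring freezing within a patient under two stimulation modes. They do justify keeping the unmodified score alongside.
- **Software.** The custom MATLAB code may already handle edges. The plan does not say so, and its written rule gives the wrong score.
- **Importance.** This is a pilot, freezing is one of several outcomes, and recruitment aims for only about half freezers (3.2.4). That limits the weight of the point, but the correction is cheap.

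**Conclusion.** The defect holds in the text. A freeze open at the end of stepping, or before the first step, is missed and scores zero, unless fewer than 20 peaks remain on one plate and the whole trial becomes a freeze. The score can jump from full trial length to zero around that cut. The errors fall more often on the condition with more freezing: 40% against 20% of trials end frozen in the example.

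In longer trials this probably attenuates the aDBS versus cDBS contrast, by about 15% at 100 s. At 60 s the loss is about a quarter or close to nil, and at 30 s the contrast can be inflated, depending on how the 20 peaks are counted. All these sizes rest on assumed stride, trial length and freeze pattern. Net direction and size cannot be fixed from the documents. The point is worth correcting before the analysis but does not threaten the trial as a whole.

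**What to change.** In section 3.2.10, item 5:

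- Treat the start and end of the stepping period as bounding extrema on both plates. Go and stop commands are described for the wrist task but not for SIP, so take the boundaries with quiet stance from the force-plate recording or the video (section 3.2.7 has all experiments videotaped).
- Test the final segment against the existing 1.2x and 2x limits. Test the initial segment against the 2x trial-mean limit only, because no three previous cycles exist there.
- Count a segment as an FE, flagged as truncated, when it exceeds the limit and is also seen visually.
- State which peaks count toward 20, the SIP trial length, and whether freezing is summarised as a count, duration or percent time.
- Apply the same rule in every condition and report the unmodified score as a sensitivity analysis.

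A 10 s edge freeze would then be an interval of at least 10 s against a mean near 1.1 s and would be found, as the same freeze in mid-trial already is. The cost is a few lines of offline code, the timing of the stepping boundaries, and a short addition to the text. The downside is small: a truncated freeze has only a minimum duration, and results will differ slightly from the unmodified algorithm.
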